3.18 Multiple Imputation Methodology

This section describes the methodology for multiple imputation for missing blood Phe data for both the DEP and RWP Periods. Based on previous studies in this indication, [FDA \(2007\)](#), it is anticipated that the amount of missing data will be relatively small (█).

3.18.1 Multiple Imputation of Blood Phe for the DEP

For sensitivity and supplementary analysis of the DEP primary and key secondary efficacy endpoint analyses, MI will be used to handle missing. The following is a summary of the Missing at Random imputation method being used for the DEP.

Missing Blood Phe values will be imputed via multiple imputation (MI) assuming MAR for each scheduled assessment visit (DEP Baseline and Week 3). Note that at each scheduled assessment visit there are duplicate blood Phe measurements and Week 3 refers to the participants last Week 3 blood Phe value at the iTD.

Fifty imputed datasets will be created.

The following are the set of variables to be used in the multiple imputation model:

- Screening blood Phe
- Previous DEP Baseline Blood Phe values. For the duplicate blood Phe measures occurring at each scheduled visit, they will be “ordered” by the corresponding vial number:
 - DEP BaselineA and DEP BaselineB
 - Week 3A and Week3B

Here the “A” values correspond to the duplicate blood Phe value with the smallest vial number and the “B” values correspond to the duplicate blood Phe value with the largest vial number. If there is just a single corresponding vial for an assessment it will be assigned “A”. Week 3 refers to the participants last Week 3 blood Phe value at the iTD.

The imputations will be performed using monotone linear regression imputation methods which will impute the participants’ blood Phe values at each of the scheduled assessment visits in the study (including the duplicate assessments at each scheduled visit).

If the missing data does not follow a monotonic pattern, a sequential approach to imputing the data via a Markov chain Monte Carlo (MCMC) method to produce a monotone missing data pattern will be applied using the MCMC impute=monotone option in Proc MI (SAS System). Then the monotone linear regression imputation methods will be applied.

Note: if the multiple imputation model does not converge or produce estimates (i.e., due to over-specification) the set of imputation variables may be modified.

Based on the multiple imputed complete blood Phe datasets, the change and percent change from baseline in blood Phe levels will be calculated and the corresponding analyses performed and combined (i.e., via MIANALYZE in SAS).

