2.5.1 Part 1: Primary and Key Secondary Efficacy Objective Estimands

The estimands corresponding to the Part 1 DEP primary and key secondary objectives and endpoints are described in [Table 4](#) and [Table 5](#), respectively.

Table 4: Estimand for the Part 1 Primary Objective

Objective	To assess the percentage change in blood Phe level
A. Population	The population is the DEP full analysis set (defined in Section 3.5) characterized by the inclusion/exclusion criteria provided in Section 4.2 of the study protocol.
B. Variable	Continuous variable: Percent change from DEP baseline in blood Phe level at the last measurement of the iTD of SYNB1934v1

C. Intercurrent events	
 Participant iTD dose is dropped: As described in Section 2.2, the participant's iTD will be the highest dose tolerated. Additionally, as described in Section 3.17, doses may be dropped at the DEP interim analysis. A treatment-policy strategy approach will be taken in that the participants DEP blood Phe levels on a dropped dose will be included in the DEP primary efficacy analysis. Treatment discontinuation: If a participant permanently discontinues study drug in the DEP, the participant will be asked to have an early termination visit 30 days after last dose of study drug (see Section 5.6 of the study protocol). Treatment discontinuation will follow the treatment-policy approach in that if the participant has reached an iTD (defined as having reached an iTD if they tolerate 3 weeks at a dose, regardless of whether other doses are tolerated) the participants DEP blood Phe levels on a dropped dose will be included in the DEP primary efficacy analysis. A Participant does not reach an iTD: A participant will be defined as having reached an iTD if they tolerate 3 weeks at a dose, regardless of whether other doses are tolerated. A participant who does reach an iTD will not have post-baseline Week 3 blood Phe level assessment. A principal stratum approach will be taken in that the target population of interest is the set of participants who reach an iTD. Antibiotic use: consistent with a treatment-policy strategy, antibiotic use will not be considered (i.e., all observed data will be used regardless of antibiotic use). Prohibited medication use: consistent with a treatment-policy strategy, prohibited medication use will not be considered (i.e., all observed data will be used regardless of prohibited medication use).

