3.5 Analysis Populations

Analysis populations will be defined for each of the 3 parts of the study (DEP, RWP, and OLE).

Full analysis set (FAS): The full analysis sets are based on the intention-to-treat principle. The DEP FAS includes all participants enrolled in the DEP who take at least one dose of DEP study medication.

The RWP FAS is defined as all participants randomized into the RWP who take at least one dose of RWP study medication. Additionally:

- The responder RWP FAS is defined as participants in the RWP FAS who are responders
- The nonresponder RWP FAS is defined as participants in the RWP FAS who are nonresponders.

A responder is defined as a participant who achieves a $\geq 20\%$ reduction in blood Phe level compared to DEP baseline on SYNB1934v1.

The responder RWP FAS will be the primary efficacy analysis population for the RWP. Analyses on the RWP FAS will be performed according to the randomized treatment group.

In the event that, based on the interim analysis results utilizing the criteria provided in [Table 10](#), the DMC recommends dropping either the 1×10^{12} or the 1×10^{12} and 6×10^{11} doses the following will occur:

- The participants in the DEP who have an iTD corresponding to a dropped dose will go directly into the OLE part of the study (i.e., as opposed to being randomized into the RWP).
- The RWP FAS, responder RWP FAS, and nonresponder RWP FAS, will exclude all participants whose iTD dose level was dropped.

These participants who are excluded from the RWP FAS will be summarized separately.

Safety analysis set (SAS): For each of the 3 study parts, the SAS will include all participants who received any amount of IMP in the corresponding study part with treatment assignment based on the treatment received.

For the RWP the safety analyses will be presented for the RWP SAS overall as well as by responder/nonresponder subgroups. Similarly, the OLE safety analyses will be presented for the OLE SAS overall as well as by responder/nonresponder subgroups.

A participant will be considered receiving treatment if the eCRF question “did the patient receive any study drug doses” is answered “Yes” and there is a corresponding non-missing date.

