3.6 Participants Disposition and Evaluability

3.6.1 Participant Disposition

The following participant disposition is summarized using the analysis populations defined in [Section 3.5](#).

- The number of participants who entered the Screening Period (i.e., as defined by signing informed consent)
- The number and percent of participants rescreened (using the number screened as the denominator).

The following percentages will use the DEP FAS as the denominator:

- The number of participants enrolled in DEP (i.e., defined as being assigned study drug)
- The number and percent of participants completing/not completing the DEP (i.e., completed the DEP is defined as having completed the End of DEP/RWP Baseline Visit as indicated in the eCRF)
- The number and percent of participants who achieve an iTD
- The number and percent of responders.

The following percentages will use the RWP FAS as the denominator:

- The number of participants randomized into the RWP overall and by responder/nonresponder status
- The number and percent of participants completing/not completing the RWP (i.e., completed the RWP is defined as having a non-missing RWP Week 4 visit) overall and by responder/nonresponder.

The following percentages will use the OLE SAS as the denominator:

- The number of participants enrolled in OLE (i.e., defined as being assigned OLE study drug)
- The number and percent of participants completing the OLE/not completing the OLE (i.e., completing the study as determined by the eCRF question “Did the subject complete the study per protocol?”).

Note: The number and percent of participants who did not complete each of the 3 study parts will be summarized along with the reason:

- LOST TO FOLLOW-UP
- PROTOCOL DEVIATION
- ADVERSE EVENT
- LOW LEVELS OF PHE OR TYR OR PROFOUND ELEVATION IN PHE
- PREGNANCY
- STUDY TERMINATED BY SPONSOR
- PHYSICIAN DECISION
- WITHDRAWAL BY SUBJECT
- NON-COMPLIANCE WITH STUDY DRUG
- DEATH
- OTHER.

The summaries will be overall for Part 1; overall, responder status, and treatment group (i.e., active or placebo) for Part 2; and overall and responder status for Part 3.

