3.14.1.3 Primary Efficacy Sensitivity and Supplementary Analysis

The following sensitivity and supplementary analyses will be performed for the primary efficacy endpoints.

- ***Analysis by iTD:*** The primary efficacy endpoint analysis will be performed on each iTD subgroup.
- ***Imputation of Missing Data:*** Multiple imputation will be used to impute missing blood Phe data during the DEP. The imputation of missing data analysis will assume the data is missing at random (MAR). The methodology for the multiple imputation is provided in [Section 3.18.1](#). As discussed in [Section 3.14.1.1](#), the imputation will not utilize the data from the DEP Weekly substudy. The analysis model will be the same model as the DEP primary efficacy endpoint analysis. The DEP FAS will be the primary efficacy analysis population for this analysis.
- ***Analysis of Covariance:*** The primary efficacy endpoint will be analyzed using an analysis of covariance (ANCOVA) model. The percent change from DEP baseline in blood Phe level at the last

measurement of the iTD of SYNB1934v1 will be the dependent variable is a factor and DEP baseline Phe is a covariate. For this analysis the 2 Phe assessments occurring at the last measurement of the iTD of SYNB1934v1 will be averaged (i.e., if just 1 Phe assessment at this timepoint, that value will be used).

Least-squares means for the percent change from baseline overall dose level, along with the corresponding █ confidence intervals and p-values testing a percent change from baseline equal to 0, will be calculated.

This will be an observed-case analysis using the DEP FAS population, missing data will not be imputed.

- ***Excluding Participants on a Dropped Dose:*** The primary efficacy endpoint analysis will be performed on the DEP FAS using an observed case analysis which excludes participants who were.
- ***Excluding Observations after Treatment Discontinuation, Antibiotic use, or Prohibited Medication:*** The primary efficacy endpoint analysis will be performed on the DEP FAS using an observed case analysis which excludes observations after the following intercurrent events occur in the DEP: Treatment discontinuation, antibiotic use, prohibited medication use.
- ***RWP PPS Analysis:*** The primary efficacy endpoint analysis will be performed using the responder DEP PPS analysis set (defined in [Section 3.5](#)).

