- ***MMRM Analysis by Dose Level:*** The change in blood Phe level will be analyzed using an MMRM model. All available Week 3 blood Phe data will be used. The model will have change from baseline as the dependent variable. Dose level (as a categorical variable) and baseline blood Phe will be fixed effects. The MMRM analysis will be based on the restricted maximum likelihood method. A Kenward-Roger approximation will be used for the denominator degrees of freedom. The covariance structure for the repeated-measures will be a direct product of unstructured for the multiple Week 3 visits (i.e., a total of 5 possible Week 3 visits, 3 for each dose level and 2 for possible repeats of the 3×10^{11} and 6×10^{11} doses) and compound symmetry for the repeated assessments at a particular visit. As such the covariance structure will use the direct product structure “UN@CS” as defined in SAS PROC Mixed.

This will be an observed-case analysis, this analysis will be performed using the DEP FAS and also using the responder RWP FAS population, missing data will not be imputed.

If the MMRM analysis does not converge, the repeated measures at each blood Phe assessment will be averaged together and the average of the repeated measures will be used to calculate the percent change in blood Phe level, the dependent variable. The model will have change from baseline as the dependent variable (i.e., using the averaged value at Week 3 visit). The MMRM model will be the same (i.e., same set of fixed effects) with the exception that the covariance structure for the repeated-measures will be unstructured for the multiple Week 3 visits (i.e., a total of 5 possible Week 3 visits, 3 for each dose level). If this model does not converge a compound symmetry covariance structure will be used.

- ***A ≥ 20% reduction from baseline in blood Phe level at any time in the DEP***

- ***Analysis by iTD:*** The analysis will be performed on each iTD subgroup.

- ***Imputation of Missing Data:*** Multiple imputation will be used to impute missing blood Phe data during the DEP. The imputation of missing data analysis will assume the data is missing at random (MAR). The methodology for the multiple imputation is provided in [Section 3.18.1](#). The number and proportion of participants meeting this criterion will be summarized along with [REDACTED] based on the imputed data. This analysis will be performed on the DEP FAS population.

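### The DEP multiple imputation is not limited to participants who reached an iTD, so it leaves the stated estimand and, for the ≥20% endpoint, credits non-attainers with response

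*SAP*

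**What the plan says.** **Estimand.** For participants who do not reach an iTD, SAP 2.5.1 (Table 4, repeated in Table 5 for the key secondary endpoints) states: "A principal stratum approach will be taken in that the target population of interest is the set of participants who reach an iTD". The same row explains that such participants have no post-baseline Week 3 Phe. The sentence has evidently lost a negative, but its sense is clear.

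**Primary analysis.** SAP 3.14.1.2 names the DEP FAS but says that only participants who reach an iTD are considered. It expects missing iTD Week 3 values to arise mainly when a sample is not analysed.

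**Imputation.** SAP 3.18.1 reads: "Missing Blood Phe values will be imputed via multiple imputation (MI) assuming MAR for each scheduled assessment visit (DEP Baseline and Week 3", and adds: "Week 3 refers to the participants last Week 3 blood Phe value at the iTD". The model variables are screening, baseline and Week 3 Phe.

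**Population for the imputation.** For the percent-change endpoint, SAP 3.14.1.3 says: "The DEP FAS will be the primary efficacy analysis population for this analysis". For absolute change and for the ≥20% endpoint, SAP 3.14.1.5 says: "This analysis will be performed on the DEP FAS population".

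**DEP FAS.** SAP 3.5: "The DEP FAS includes all participants enrolled in the DEP who take at least one dose of DEP study medication". SAP 3.6.1 uses this set as the denominator for "The number and percent of participants who achieve an iTD", so it is wider than the attainers.

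**Main ≥20% analysis.** SAP 3.14.1.4 uses the DEP FAS and counts participants who lack the necessary data as not meeting the endpoint.

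**The concern.** A participant who never tolerated three weeks at any dose is in the DEP FAS, has no iTD, and so has no Week 3 value at the iTD. Under 3.18.1 as written that empty cell is a missing Week 3 value and is filled. Every observed Week 3 value feeding the regression comes from someone who tolerated three weeks on drug, and the model has no term for iTD attainment, tolerability or discontinuation. The non-attainer therefore receives an on-drug value for a state that did not occur.

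Two things are at stake. First, a sensitivity analysis should keep the primary estimand and vary the missing-data assumption. This one also widens the population, so agreement with the primary result says little about unanalysed samples. Second, the imputed ≥20% analysis replaces not met by imputed response for the same people, which raises the proportion. The DEP has no imputation under a less favourable assumption to set against this. The placebo-based MNAR imputation in SAP 3.18.2.2 applies only to the RWP.

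**Working it through.** **The plan's own figure.** The documents give no expected iTD attainment rate and no forecast for the imputed analyses. The one DEP figure is power of over 98% (Protocol synopsis, Sample Size Considerations). The sample size is redacted, so it cannot be reproduced. A one-sample t-test with mean -11%, SD 17% and two-sided 0.05 needs 41 evaluable participants (98.1%), and 41/0.9 = 45.6, so 46 enrolled. This has no bearing on the point.

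**Inputs**
- From the Protocol synopsis: mean percent change -11%, SD 17%, about 50% responders, 10% DEP dropout.
- Assumed: non-attainment of 10% (borrowing the dropout figure) and 30% (illustrative, with no source in the documents).
- Attainers' response rate p, two values: 50%, taking the Protocol's figure to apply to attainers, and the rate implied by a normal percent change with the Protocol's mean and SD, P(change ≤ -20%) = Φ((-20 + 11)/17) = Φ(-0.53) = 29.8%.

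**≥20% endpoint.** Let a be the proportion of the FAS reaching an iTD.
- Main analysis, missing = not met: a × p.
- Imputation over the whole FAS: a × p + (1 - a) × p ≈ p, if non-attainers resemble attainers on screening and baseline Phe.
- Rise: (1 - a) × p.

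| Non-attainment | p | Main analysis | Imputed on FAS | Rise (points) |
|---|---|---|---|---|
| 10% | 50% | 0.9 × 50 = 45% | 50% | 5 |
| 10% | 29.8% | 0.9 × 29.8 = 26.8% | 29.8% | 3.0 |
| 30% | 50% | 0.7 × 50 = 35% | 50% | 15 |
| 30% | 29.8% | 0.7 × 29.8 = 20.9% | 29.8% | 8.9 |

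**Simulation check.** The imputation rule was simulated in simplified form: one value per visit, 100 FAS participants, 50 imputations, 400 replicates. Assumed were a baseline median of 900 µmol/L, log-SD 0.35, normal percent change, and non-attainers like attainers at baseline. With mean -11% and SD 17%, non-attainers were credited with response in 31.8% of imputations at 10% non-attainment and 31.6% at 30%, against 29.9% and 29.6% observed among attainers. The FAS proportion rose from 26.9% to 30.1% and from 20.7% to 30.2%. With the mean set to -20%, so that about half of attainers respond, it rose from 45.3% to 50.3% and from 35.0% to 50.0%. This agrees with the table.

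**Mean percent change.** In the same simulation the imputed FAS mean was -11.2% against -11.2% among attainers at 10% non-attainment, and -10.95% against -10.95% at 30%. The imputation reproduces the attainers' mean, so the figure is close to the target but agreement is largely built in.

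**The case against.** The strongest reply is that no sentence says non-attainers are imputed. The imputed quantity is defined at the iTD, and a person without an iTD has nothing there to be missing. SAP 3.14.1.2 also uses the label DEP FAS while considering attainers only, and SAP 3.18 expects little missing data. For the two continuous endpoints this reading is possible, though 3.14.1.3, 3.14.1.5 and 3.18.1 do not state it. For the ≥20% endpoint it does not hold: 3.14.1.4 scores participants without data as failures on the DEP FAS, so non-attainers are in that set, and 3.14.1.5 keeps the set and substitutes imputed values.

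The reply is right on several stronger inferences a reader might draw:
- **That the mean effect is inflated.** Giving non-attainers zero change would yield -11% × 0.9 = -9.9%, or -11% × 0.7 = -7.7%. The plan does not specify that target. Its target is the attainers' mean, which the imputation returns.
- **That the imputed proportion overshoots its own estimand.** Table 5 applies the attainers-only stratum to the ≥20% endpoint too, so the target there is p. In this comparison it is the main FAS analysis that departs from it. The rise exists only relative to that main analysis.
- **That those credited are intolerant, or are nearly all of those imputed.** SAP 3.6.1 lists many other reasons for leaving, and 3.18.1 also fills missing baselines and duplicates.
- **That primary evidence is affected.** These are sensitivity or supplementary analyses. The dichotomous DEP endpoint has no inferential test (SAP 3.14.1.6), and SAP 2.1 places the primary evidence of efficacy in the RWP comparison.

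**Conclusion.** The point holds as a scope defect in the DEP imputation. As written, it covers the DEP FAS without restriction, while the estimand covers only participants who reach an iTD. For percent and absolute change, no material numerical bias is shown if non-attainers resemble attainers at baseline; the loss is that the analysis is not a clean check of the primary estimand. For the ≥20% endpoint, non-attainers are credited at about the attainers' rate, adding roughly 3 to 5 points at 10% non-attainment and 9 to 15 points at 30%, relative to the main analysis on the same FAS.

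These sizes rest on assumed rates. Dropout is not non-attainment, since a participant who leaves after tolerating three weeks at a dose already has an iTD. The Protocol does not say whether its 50% refers to attainers or to everyone, and 50% does not fit a normal change with mean -11% and SD 17%. The DEP primary test and the responder set used in the RWP are unaffected. The change is worth making because it is cheap and the ≥20% figure would otherwise be read as robustness.

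**What to change.** In SAP 3.18.1, and by reference in 3.14.1.3 and 3.14.1.5:

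1. For percent change and absolute change, limit the DEP imputation and its analysis to participants who reached an iTD, imputing only a missing baseline or iTD Week 3 value, or a missing duplicate of either.
2. For the ≥20% endpoint, apply the same limit to what is imputed. With the DEP FAS as denominator, keep non-attainers as not meeting the endpoint, to match 3.14.1.4. Also report the proportion among iTD attainers, to match Table 5.
3. If FAS-wide imputation is wanted as well, label it supplementary and state its own estimand.

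The cost is a few sentences of SAP text and a somewhat less favourable sensitivity figure for the ≥20% endpoint. No data collection or sample size changes.

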3.18.2 Multiple Imputation of Blood Phe for the RWP

For sensitivity and supplementary analysis of the RWP primary and key secondary efficacy endpoint analyses, MI methods will be used to handle missing. The following is a summary of the two imputation methods being used in the RWP, Missing at Random (MAR) and Missing Not at Random (MNAR).

The MAR and MNAR MI will each create 50 imputed datasets. The imputed datasets will be analyzed using the specified primary or key secondary efficacy endpoint analysis methodology. The results across the multiple imputed data sets will be combined using SAS Proc MIANALYZE.

3.18.2.1 Missing at Random Multiple Imputation

Missing Blood Phe values will be imputed via multiple imputation (MI) assuming MAR for each of the following assessment visits (DEP Screening, DEP Baseline, RWP Baseline, RWP Week 1, RWP Week 3, and RWP Week 4). Note that at each scheduled assessment visit there are duplicate blood Phe measurements.

Fifty imputed datasets will be created.

The following are the set of variables to be used in the multiple imputation model:

- DEP Screening blood Phe
- DEP Baseline blood Phe (i.e., using the average of the duplicate values)
- iTD Dose level
- Randomized Treatment group (SYNB1934v1 or placebo)
- Previous RWP Baseline blood Phe values. For the duplicate blood Phe measures occurring at each scheduled visit, they will be “ordered” by the corresponding vial number:
 - RWP BaselineA and RWP BaselineB
 - Week 1A and Week1B
 - Week 3A and Week3B
 - Week 4A and Week4B

Here the “A” values correspond to the duplicate blood Phe value with the smallest vial number and the “B” values correspond to the duplicate blood Phe value with the largest vial number. If there is just a single corresponding vial for an assessment it will be assigned “A”.

The imputations will be performed using monotone linear regression imputation methods which will impute the participants’ blood Phe values at each of the scheduled assessment visits in the study (including the duplicate assessments at each scheduled visit).

If the missing data does not follow a monotonic pattern, a sequential approach to imputing the data via a Markov chain Monte Carlo (MCMC) method to produce a monotone missing data pattern will be applied using the MCMC impute=monotone option in Proc MI (SAS System). Following the method described in [Smith \(2017\)](#) the non-monotonic data imputation will be performed “by” the categorical treatment group variable. Then the monotone linear regression imputation methods will be applied.

Note: if the multiple imputation model does not converge or produce estimates (i.e., due to over-specification) the set of imputation variables may be modified.

Based on the complete Blood Phe datasets, the change and percent change from baseline in blood Phe levels will be calculated.

